6.4. Study Intervention Compliance

Participants will receive study intervention directly from the investigator or qualified designee, under medical supervision. The date and time of dosing will be recorded in the source documents and recorded in the case report form (CRF).

6.5. Concomitant Therapy

Concomitant Therapy

Participants should be treated according to standard of care, even as it evolves, and medications may be part of the treatment paradigm.

Remdesivir may be initiated as standard of care for participants requiring hospitalization.

If the local standard of care per written policies or guidelines (that is, not just an individual clinician decision) includes investigational agents to treat COVID-19, then starting these during the study is permitted, but may require additional safety monitoring.

Convalescent COVID-19 plasma treatment is not allowed, except in hospitalized participants.

Vaccines for SARS-CoV-2 should not be used prior to Week 8 of the evaluation period for the prevention cohort of Part 2.

Any medication, investigational agent, or vaccine, including over the counter or prescription medicines, vitamins, and/or herbal supplements, or other specific categories of interest (such as convalescent COVID-19 plasma treatment) that the participant is receiving at the time of enrollment or receives during the study must be recorded along with

- Reason for use
- Dates of administration including start and end dates, and
- Dosage information including dose and frequency for concomitant therapy of special interest.

Acetaminophen and corticosteroid use are permitted at any time during the study.

Other concomitant medication may be considered on a case-by-case basis by the investigator in consultation with the sponsor if required.

The sponsor should be contacted if there are any questions regarding concomitant or prior therapy.

6.6. Intervention after the End of the Study

No continued access is planned after completion of this study, as additional efficacy would be needed to demonstrate continued access criteria.

7. Discontinuation of Study Intervention and Participant Discontinuation/Withdrawal

These sections describe reasons for a participant's

- permanent or temporary discontinuation of study drug, or
- discontinuation (withdrawal) from the study.

Discontinuation of specific sites or of the trial as a whole are handled as part of regulatory, ethical, and trial oversight considerations in Section [10.1.9](#). Appendix 1.

7.1. Discontinuation of Study Intervention

In rare instances, it may be necessary for a participant to permanently discontinue (definitive discontinuation) study intervention. If study intervention is definitively discontinued, the participant will remain in the study for follow-up and any further evaluations as described in the SoA.

7.2. Participant Discontinuation/Withdrawal from the Study

A participant may withdraw from the study:

- at any time at his/her own request
- at the request of his/her designee (for example, legal authorized representative)
- at the discretion of the investigator for safety, behavioral, compliance, or administrative reasons
- if the participant becomes pregnant during the study
- if enrollment in any other clinical study involving an investigational product or enrollment in any other type of medical research judged not to be scientifically or medically compatible with this study

Discontinuation is expected to be uncommon.

At the time of discontinuing from the study, if possible, an early discontinuation visit should be conducted, as shown in the SoA. See the SoA for data to be collected at the time of study discontinuation and follow-up and for any further evaluations that need to be completed. The participant will be permanently discontinued both from the study intervention and from the study at that time.

If the participant, or the participant's legal authorized representative, withdraws consent for disclosure of future information, the sponsor may retain and continue to use any data collected before such a withdrawal of consent. If a participant withdraws from the study, he/she or the participant's legal authorized representative, may request destruction of any samples taken and not tested, and the investigator must document this in the site study records.

7.2.1. Discontinuation of Inadvertently Enrolled Participants

If the sponsor or investigator identify a participant who did not meet enrollment criteria and was inadvertently enrolled, then the participant should be discontinued from study intervention unless

there are extenuating circumstances that make it medically necessary for the participant to continue study intervention.

If the investigator and the sponsor CRP/CRS agree it is medically appropriate to continue, the investigator must obtain documented approval from the sponsor CRP/CRS to allow the inadvertently enrolled participant to continue in the study with or without treatment with investigational product.

Safety follow up is as outlined in

- Section 1.3 (Schedule of Activities)
- Section 8.2 (Safety Assessments), and
- Section 8.3 (Adverse Events and Serious Adverse Events).

7.3. Lost to Follow up

A participant will be considered lost to follow-up if he or she repeatedly fails to return for scheduled visits and is unable to be contacted by the study site. Site personnel are expected to make diligent attempts to contact participants who fail to return for a scheduled visit or were otherwise unable to be followed up by the site.

Site personnel, or an independent third party, will attempt to collect the vital status of the participant within legal and ethical boundaries for all participants who received investigational product. Public sources may be searched for vital status information. If vital status is determined to be deceased, this will be documented and the participant will not be considered lost to follow-up. Sponsor personnel will not be involved in any attempts to collect vital status information.

8. Study Assessments and Procedures

Study procedures and their timing are summarized in the SoA.

Protocol waivers or exemptions are not allowed.

Monitoring of blinded safety data will continue throughout the study and will be conducted by blinded study team members. Details of the blinded safety reviews, including the frequency and approximate timing, are specified in the trial level safety review plan.

Immediate safety concerns should be discussed with the sponsor immediately upon occurrence or awareness to determine if the participant should continue or discontinue study intervention.

Adherence to the study design requirements, including those specified in the SoA, is essential and required for study conduct.

All screening evaluations must be completed and reviewed to confirm that potential participants meet all eligibility criteria. The investigator will maintain a screening log to record details of all participants screened and to confirm eligibility or record reasons for screening failure, as applicable.

8.1. Efficacy Assessments

8.1.1. SARS-CoV-2 Viral Swab and Serology

For details concerning viral swab, see Pharmacodynamics (Section 8.6). In Part 1, any positive result from a baseline SARS-CoV-2 test (NP or nasal swab) will result in the participant being declared SARS-CoV-2 positive in the analysis populations. In Part 2, the result from the screening POC test and baseline SARS-CoV-2 test are planned to be used to define SARS-CoV-2 status for the analysis populations.

Nasal swabs are planned during the evaluation and post-evaluation period at times described in the SoA. However, in the event nasal swabs cannot be supplied, the Sponsor may substitute with oropharyngeal, mid-turbinate or nasopharyngeal swabs. For instructions related to performing the nasopharyngeal, mid-turbinate, nasal, or oropharyngeal, swab, see guidance provided by Sponsor.

For Part 3, any positive result from a baseline SARS-CoV-2 test (NP) will result in the participant being declared SARS-CoV-2 positive in the analysis populations. NP swabs are planned during the evaluation and post-evaluation period at times described in the SoA.

For details concerning viral serology, see Pharmacodynamics (Section 8.6).

8.1.2. Participant Symptoms Questionnaire

Participants will be asked about the presence or absence of symptoms and signs associated with COVID-19 experienced during the past 24 hours, at the timepoints described in the SoA.

Signs and symptoms associated with COVID-19 should not be captured as AEs, unless more severe than expected. See Section 10.3.1. for additional information AE definitions used in this study.

Symptoms include

- shortness of breath with movement
- shortness of breath at rest
- cough
- chest pain or discomfort with breathing
- feeling feverish
- chills
- sore throat
- muscle or body aches and pain
- fatigue or loss of energy
- headache
- nausea
- diarrhea
- vomiting
- loss of appetite
- loss of taste, and
- loss of smell.

Participants requiring a legally authorized representative to provide signed informed consent will not be asked to report the presence or absence of symptoms. Only symptoms that may be observed by site staff other than the participant will be recorded, including

- shortness of breath with movement
- shortness of breath at rest
- cough
- diarrhea, and
- vomiting.

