6.1.1.2. Management of Infusion Reactions

All participants should be monitored closely, as there is a risk of infusion reaction and hypersensitivity (including anaphylaxis) with any biological agent.

Symptoms and Signs

Symptoms and signs that may occur as part of an infusion reaction include, but are not limited to fever, chills, nausea, headache, bronchospasm, hypotension, angioedema, throat irritation, rash including urticaria, pruritus, myalgia, and dizziness.

Infusion-related reactions severity will be assessed and reported using the Division of AIDS (DAIDS) Table for Grading the Severity of Adult and Pediatric Adverse Events, Corrected Version 2.1 (July 2017).

This table describes the severity of reactions according to DAIDS.

Parameter	Mild	Moderate	Severe	Severe and Potentially Life-threatening
Acute Allergic Reaction	Localized urticaria (wheals) with no medical intervention indicated	Localized urticaria with intervention indicated OR Mild angioedema with no intervention indicated	Generalized Urticaria OR Angioedema with intervention indicated OR Symptoms of mild bronchospasm	Acute anaphylaxis OR Life-threatening bronchospasm OR Laryngeal edema
Cytokine Release Syndrome ^a	Mild signs and symptoms AND Therapy (that is, antibody infusion) interruption not indicated	Therapy (that is, antibody infusion) interruption indicated AND Responds promptly to symptomatic treatment OR	Prolonged severe signs and symptoms OR Recurrence of symptoms following initial improvement	Life-threatening consequences (for example, requiring pressor or ventilator support)

		Prophylactic medications indicated for ≤ 24 hours		
--	--	--	--	--

^a A disorder characterized by nausea, headache, tachycardia, hypotension, rash, and/or shortness of breath.

Source: DAIDS Table for Grading the Severity of Adult and Pediatric Adverse Events, Corrected Version 2.1 (July 2017).

Site Needs

The clinical site should have necessary equipment and medications for the management of any infusion reaction, which may include but is not limited to oxygen, IV fluids, epinephrine, acetaminophen and antihistamine.

Management of Infusion Reactions

Investigators should determine the severity of the infusion reaction and manage infusion reactions based on standard of care and their clinical judgment. If an infusion reaction occurs, then supportive care should be used in accordance with the signs and symptoms.

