10.2. Appendix 2: Clinical Laboratory Tests

Clinical laboratory tests will be performed according to the SoA.

Additional tests may be performed at any time during the study as determined necessary by the investigator or required by local regulations.

Central and local laboratories will be used. The SoA and table below describes when the local or central laboratory will be used.

Laboratory results that could unblind the study will not be reported to investigative sites or other blinded personnel.

Protocol-specific requirements for inclusion or exclusion of participants are detailed in Section 5 of the protocol.

Pregnancy testing will be performed according to the SoA.

Investigators must document their review of laboratory safety results.

Refer to Section 10.6, Appendix 6, for recommended laboratory testing for hypersensitivity events.

Clinical Laboratory Tests	Comments
Hematology	Assayed by Lilly-designated laboratory
Hemoglobin	
Hematocrit	
Erythrocyte count (Red Blood Cells - RBCs)	
Mean cell volume	
Mean cell hemoglobin	
Leukocytes (White Blood Cells - WBCs)	
Differential	
Neutrophils, segmented	
Lymphocytes	
Monocytes	
Eosinophils	
Basophils	
Platelets	
Cell Morphology (RBC and WBC)	
Clinical Chemistry	Assayed by Lilly-designated laboratory
Sodium	
Potassium	
Chloride	
Bicarbonate	
Total bilirubin	
Direct bilirubin	
Alkaline phosphatase (ALP)	
Alanine aminotransferase (ALT)	
Aspartate aminotransferase (AST)	
Gamma-glutamyl transferase (GGT)	
Blood urea nitrogen (BUN)	
Creatinine	
Creatine kinase (CK)	
Uric acid	
Total protein	
Albumin	
Calcium	
Phosphorus	
Glucose	
Amylase	
Lipase	
Lactate dehydrogenase (LDH)	

Clinical Laboratory Tests	Comments
Calculations	
eGFR	calculated by CKD-EPI equation. Calculated by Lilly-designated laboratory. Results will not be provided to the investigative sites.
SARS-CoV-2 Panel	
C-Reactive Protein	
Ferritin	
D-dimer	
Procalcitonin	
Troponin	
Hormones (female)	
Urine Pregnancy	Local laboratory
Pharmacokinetic Samples	Assayed by Lilly-designated laboratory. Results will not be provided to the investigative sites.
Pharmacodynamic sample	Assayed by Lilly-designated laboratory.
SARS-CoV-2 swab (nasopharyngeal, mid-turbinate, nasal, or oropharyngeal)	Negative results will not be provided to the investigative sites.
SARS-CoV-2 Serology	Assayed by Lilly-designated laboratory. Results will not be provided to the investigative sites.

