10.3.1. Definition of AE

AE Definition

- An AE is any untoward medical occurrence in a patient or clinical study participant, temporally associated with the use of study intervention, whether or not considered related to the study intervention.
- NOTE: An AE can therefore be any unfavorable and unintended sign (including an abnormal laboratory finding), symptom, or disease (new or exacerbated) temporally associated with the use of study intervention.

Events Meeting the AE Definition

- Any abnormal laboratory test results (hematology, clinical chemistry, or urinalysis) or other safety assessments (e.g., electrocardiogram, radiological scans, vital signs measurements), including those that worsen from baseline, considered clinically significant in the medical and scientific judgment of the investigator (i.e., not related to progression of underlying disease).
- Exacerbation of a chronic or intermittent pre-existing condition including either an increase in frequency and/or intensity of the condition.
- New conditions detected or diagnosed after study intervention administration even though it may have been present before the start of the study.
- Signs, symptoms, or the clinical sequelae of a suspected drug-drug interaction.
- Signs, symptoms, or the clinical sequelae of a suspected overdose of either study intervention or a concomitant medication. Overdose per se will not be reported as an AE/SAE unless it is an intentional overdose taken with possible suicidal/self-harming intent. Such overdose should be reported regardless of sequelae.
- “Lack of efficacy” or “failure of expected pharmacological action” per se will not be reported as an AE or SAE. Such instances will be captured in the efficacy assessments. However, the signs, symptoms, and/or clinical sequelae resulting from lack of efficacy will be reported as AE or SAE if they fulfill the definition of an AE or SAE.

Events NOT Meeting the AE Definition

- The following study-specific clinical events related to COVID-19 are exempt from adverse event reporting unless the investigator deems the event to be related to the administration of study drug:
 - Hypoxemia due to COVID-19 requiring supplemental oxygen;
 - Hypoxemia due to COVID-19 requiring non-invasive ventilation or high flow oxygen devices;

- Respiratory failure due to COVID-19 requiring invasive mechanical ventilation or ECMO

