- Any clinically significant abnormal laboratory findings or other abnormal safety assessments which are associated with the underlying disease, unless judged by the investigator to be more severe than expected for the participant's condition.
- The disease/disorder being studied or expected progression, signs, or symptoms of the disease/disorder being studied, unless more severe than expected for the participant's condition.
- Medical or surgical procedure (e.g., endoscopy, appendectomy): the condition that leads to the procedure is the AE.
- Situations in which an untoward medical occurrence did not occur (social and/or convenience admission to a hospital).
- Anticipated day-to-day fluctuations of pre-existing disease(s) or condition(s) present or detected at the start of the study that do not worsen.

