### **6.12.3. Adverse Events**

Summaries of AEs will include the number of patients with at least 1 AE for each treatment group. When reporting by System Organ Class (SOC) and PT, the reports will present the SOC in alphabetical order; while PTs within the SOC will be presented in order of overall decreasing frequency of occurrence overall. A patient with multiple AEs (different PTs) coded to the same SOC will be counted only once for that SOC, but will be counted each time for different PTs within that SOC. A patient with separate events of the same PT will be counted only once in the frequency tables for that PT.

Adverse events will be coded according to the Medical Dictionary for Regulatory Activities (MedDRA) and summarized by SOC, PT, severity, and relationship to IP as assessed by the investigator. For each event classification term, the number of subjects experiencing a treatment-emergent AE (TEAE) with that classification term will be tabulated.

In an overview table, the number and percentage of patients who experienced a TEAE, serious adverse event (SAE), AE related to study drug, died due to an AE, discontinued from the study treatment, or discontinued from the study due to an AE will be summarized by treatment.

Treatment-emergent AEs may be reported separately for the evaluation period and follow-up period.

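### Section 8.1.2 exempts COVID-19-type symptoms from AE recording without requiring infection, so drug-related symptoms in uninfected Prevention participants may be under-recorded or recorded inconsistently

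*Protocol*

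**What the plan says.** Protocol Section 8.1.2 describes a 16-item questionnaire on symptoms and signs associated with COVID-19. Under the schedule in Section 1.3.1 it is completed daily through the evaluation period in Part 1 and the Part 2 Prevention Cohort. The same section then states: "Signs and symptoms associated with COVID-19 should not be captured as AEs, unless more severe than expected". It adds: "See Section 10.3.1. for additional information AE definitions used in this study".

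Section 10.3.1 starts broadly: "An AE is any untoward medical occurrence in a patient or clinical study participant, temporally associated with the use of study intervention". Relatedness is not required. Among the events that are not AEs it lists "The disease/disorder being studied or expected progression, signs, or symptoms of the disease/disorder being studied", unless these are more severe than expected for that participant's condition.

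Section 6.1.1.2 names possible infusion-reaction symptoms: "fever, chills, nausea, headache, bronchospasm, hypotension, angioedema, throat irritation, rash including urticaria, pruritus, myalgia, and dizziness".

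On swab results, Section 10.2 says: "Negative results will not be provided to the investigative sites".

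SAP Section 6.12.3 builds the safety comparison on recorded AEs: for each term, "the number of subjects experiencing a treatment-emergent AE (TEAE) with that classification term will be tabulated".

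**The concern.** The phrase that describes the questionnaire is also the phrase that describes what to leave off the AE form. A site would naturally read this as saying that questionnaire items are not AEs. Nothing in the sentence restricts it to people with COVID-19, and its escape clause (worse than expected) has no reference state in someone who is not infected.

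Most Prevention participants are expected to be uninfected, and the antibody's plausible common side effects overlap heavily with the questionnaire. If sites follow 8.1.2 literally, mild drug-related symptoms may be missing from the AE data. If some sites follow 8.1.2 and others 10.3.1, recording will vary by site. Either way, the by-arm safety comparison in a prophylaxis trial becomes less sensitive to the effects it should be able to show.

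**Working it through.** The plan states no figure on this point, so the check is mainly a comparison of passages.

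**1. Scope of the two exemptions.** Section 8.1.2 covers symptoms associated with COVID-19, with no condition on test status. Section 10.3.1 covers signs or symptoms of the disease under study, judged against the participant's own condition. A headache in an uninfected person is exempt on a literal reading of the first and an AE under the second. Section 8.1.2 cites 10.3.1 for further information and does not say which governs.

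**2. Override for drug-related events.** Section 10.3.1 keeps events reportable when the investigator judges them drug-related, but attaches this only to hypoxemia and respiratory failure due to COVID-19. It does not mention the questionnaire symptoms.

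**3. Overlap with expected drug reactions.** Of the 12 symptoms in the 6.1.1.2 list, six match questionnaire items: fever, chills, nausea, headache, throat irritation (sore throat, a near match) and myalgia. Shortness of breath, in the cytokine-release footnote, is a seventh overlap.

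**4. Reach of the infusion-reaction route.** Sections 8.3.6 and 8.3.7 send recognised reactions to the CRF, and 10.3.3 grades them as AEs. Section 8.3.6 covers symptoms during or within 6 hours of infusion that are believed to be hypersensitivity or cytokine release. Section 8.3.7 sets no time limit but still requires recognition as infusion-related. Section 4.3 gives a half-life of about 19 days, so exposure far outlasts 6 hours.

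**5. Who is affected.** Part 1 plans about 1300 baseline-negative participants out of 1700 (1300/1700 = 76%). The assumed 8-week placebo rate of moderate-or-worse COVID-19 is 4.0% in Part 1 and 5.3% in Part 2. No rate for all infections is assumed, so the statement that most stay uninfected is an inference from these figures.

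**6. Other by-arm displays.** SAP 6.12 contains no questionnaire table, and the DSMB data list in SAP 6.15.1 does not include the questionnaire. Temperature is covered by the vital-sign analyses in SAP 6.12.7.

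**7. Illustration with assumed rates.** Take n = 600 uninfected per arm (Part 1 plans 1300/2 = 650 baseline-negative per arm). Let p1 and p0 be the true symptom rates on active drug and placebo, and d = p1 − p0. With full recording, SE = √[(p1(1−p1) + p0(1−p0))/n].

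- 10% vs 5%: 30 extra cases; SE = √[(0.0900 + 0.0475)/600] = 0.0151; difference 5.0 points (95% CI 2.0 to 8.0); z = 3.3.
- 6% vs 3%: 18 extra cases; SE = √[(0.0564 + 0.0291)/600] = 0.0119; z = 2.5.

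If both arms record only a fraction c of cases, the rates become c·p1 and c·p0. Setting z = 1.96 and solving gives c = 1.96²(p1 + p0) / [n·d² + 1.96²(p1² + p0²)].

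- 10% vs 5%: c = 0.576/(1.500 + 0.048) = 0.37.
- 6% vs 3%: c = 0.346/(0.540 + 0.017) = 0.62.

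Under these assumptions, the difference falls below the conventional threshold once fewer than about 37% or 62% of cases are recorded. This shows how equal under-recording weakens a comparison. It does not estimate how much under-recording will occur.

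**The case against.** The strongest reply is that the governing AE definition lies elsewhere and is sound. Section 8.1.2 points to 10.3.1, the schedule of activities defines AEs by Section 10.3, and 8.3.1 requires all AEs to be collected. On the 10.3.1 wording, a drug-caused symptom in an uninfected person is an AE. Headache, nausea, chills, fever and myalgia are all named infusion-reaction symptoms, are watched for during the infusion and at least 1 hour after it, and reach the AE data when recognised. The SAP has no carve-out for COVID-type terms.

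This stands against a stronger reading. From 8.1.2 alone a reader might infer that the protocol bars these symptoms outright, that they never reach the TEAE tables, and that both arms would report about zero. The documents do not support that: 10.3.1 limits the exemption, recognised infusion reactions are recorded and graded as AEs, and temperature is measured daily and analysed by arm.

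Two further replies stand in part.

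- Only negative swab results are withheld. Positive results can reach sites, so with weekly swabs the absence of a positive report carries some information, though late. Part 2 Prevention participants also have a negative point-of-care result before randomization. This weakens the point about site knowledge but does not remove it, especially in Part 1 and for later symptoms.
- The questionnaire is not put to everyone. For participants consented through a representative, only five observable items are recorded, and none is headache, nausea, chills, feverishness or myalgia. The Part 2 Treatment Cohort and Part 3 schedule has no questionnaire.

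The reply does not remove the conflict between 8.1.2 and 10.3.1, the missing override for these symptoms, or the lack of a by-arm questionnaire display as a backstop.

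**Conclusion.** The point holds as an unresolved conflict between 8.1.2 and 10.3.1 that risks incomplete and inconsistent AE recording. It concerns drug-related symptoms, typically mild and arising after the infusion period, in uninfected participants of Part 1 and the Part 2 Prevention Cohort, when they are not recognised as infusion reactions. It is not a categorical loss of safety data.

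The amount lost cannot be derived from the documents, because it depends on which section each investigator follows. Blinding should make the loss similar between arms. That limits bias in relative comparisons but still shrinks the absolute excess and the power to detect it. The conclusion assumes that at least some sites will take 8.1.2 at its word. The change is worth making because the wording is easy to correct and the symptom data are already collected.

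**What to change.** 1. **Protocol 8.1.2.** State that the AE exemption applies only to participants with a positive SARS-CoV-2 test, and not to events judged related to study intervention. Reconcile 10.3.1 with this: it currently contains no test condition, and its relatedness override does not reach these symptoms.

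2. **SAP 6.12.** Add a by-arm table of questionnaire symptoms that are new since the pre-dose record, through Day 8 and through Day 57, excluding time after a positive test. Restrict it to Part 1 and the Part 2 Prevention Cohort within the Safety populations, since no questionnaire is scheduled elsewhere. Add a sensitivity version that also drops symptoms in the week before the first positive swab. Swabs are weekly, so early COVID-19 symptoms can precede a positive result; if the drug works, these would fall more on placebo and could mask a drug excess. Show participants consented through a representative separately, because only five observable items are recorded for them.

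The cost is a short protocol clarification and one table, with its sensitivity version, from data already captured daily. The downsides are more AE entry at sites, and some early COVID-19 symptoms recorded as AEs before a positive result is known.
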